### 1.1.5.3 Safety

The main body of safety data in patients with schizophrenia comes from the MAD study (study 14754A) which has been completed. The other study in patients with schizophrenia, the ongoing PET study (study 15859A), is still blinded.

In the MAD study, the adverse events with the highest incidence (>10%) in the Lu AF35700 groups in the daily dosing cohorts were: somnolence (33%), anxiety (23%), headache (21%, placebo level), orthostatic hypotension (19%), dizziness (16%), psychotic disorder (14%), and akathisia (11%). In the once-weekly dosing cohorts the adverse events occurring in

≥2 patients in the Lu AF35700 groups were (number of patients out of 12): somnolence (5), constipation (4), insomnia (3), anxiety (2), and musculoskeletal pain (2). In total there was 1 serious adverse event, increased psychosis, which necessitated hospitalisation of the patient. The patient recovered after 9 days after treatment with paliperidone. The investigator assessed the causality as *not related* to the investigational medicinal product (IMP). All non-serious adverse events were of *mild* to *moderate* intensity, with the exception of one event of *severe* somnolence which resolved after a few hours. The blinded data from the ongoing PET study showed that anxiety, insomnia, and headache have been reported as adverse events in that study.

Please refer to the *Investigator Brochure* for a summary of the TEAEs with the highest incidence in MAD study 14754A.

In the MAD study, an explorative analysis of the effect of treatment on QTcf indicated a treatment and dose-related trend for QTcf prolongation. None of the patients in the study had any symptoms or QTcf values that met the potentially clinically significant (PCS) criterion (>500 ms or >60 ms increase from baseline) and no observations from ECG or cardiac telemetry were reported as adverse events.

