20. The patient has orthostatic hypotension (defined as a decrease in systolic blood pressure >20 mmHg between two measurements, first in the supine position and then sitting, and standing after the patient has rested in each position for at least 3 minutes.
  21. The patient has, based on the last available ECG measurement taken during study 16159A:
    - an abnormal ECG that is, in the investigator’s opinion, clinically significant
    - a PR interval >250 ms
    - a QRS interval >130 ms
    - a QTcF interval >450 ms (for men) or >470 ms (for women) (based on the Fridericia correction where  $QTcF = QT/RR^{0.33}$ )
    - A patient should also be excluded if he or she has any other abnormal ECG tests that in the investigator’s clinical judgement are medically significant and would impact the safety of the patient or the interpretation of the study results.

For patients who completed the dosing period of study 16323A

General

1. The patient has previously been enrolled in this study.
2. The patient is a member of the study personnel or of their immediate families, or is a subordinate (or immediate family member of a subordinate) to any of the study personnel.
3. The patient has developed a severe drug allergy or hypersensitivity to the IMP or its excipients during study 16323A.
4. The patient is, in the investigator’s opinion, unlikely to comply with the protocol or is unsuitable for any reason.

Psychiatric

5. The patient has been diagnosed with a primary psychiatric disorder other than schizophrenia during study 16323A.
6. The patient has a clinically significant unstable illness diagnosed during study 16323A.
7. The patient is experiencing an acute exacerbation of his/her psychotic symptoms according to the investigator’s clinical judgement.
8. The patient has a current diagnosis of substance use disorder according to DSM 5TM criteria during study 16323A with the exception of tobacco, or mild cannabis or mild alcohol use disorder. Patients with a positive drug screen test at the Baseline Visit, with the exception of cannabis and verified by repeated testing, are excluded from the study.
9. The patient, in the opinion of the investigator, is at significant risk of suicide, or the patient:
  - Answers “Yes” to any question on the Suicidal Behaviour section of the C-SSRS, OR
  - Answers “Yes” to questions 4 and 5 on the Suicidal Ideation section of the C-SSRS.

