## 5.4 Withdrawal Criteria

A patient must be withdrawn from the study if:

- the patient and/or his or her legal representative (if applicable) withdraw(s) his or her consent (defined as a patient and/or his or her legal representative [if applicable] who explicitly take(s) back his or her consent); section 8.4 states how the patient's data will be handled
- the patient is lost to follow-up (defined as a patient who fails to comply with scheduled study visits or contact, who has not actively withdrawn from the study, and for whom no alternative contact information is available [this implies that at least two documented attempts have been made to contact the patient via both phone and mail]).

A patient must be withdrawn from treatment if:

- the investigator considers it, for safety, lack of efficacy, and/or study compliance reasons, in the best interests of the patient that he or she be withdrawn
- the patient becomes pregnant
- the patient has a serum ALT or AST value >3 times the upper limit of the reference range and a serum total bilirubin value >2 times the upper limit of the reference range
- the patient has a serum ALT or AST value >5 times the upper limit of the reference range that is confirmed by testing <2 weeks later
- the patient has a QTcF interval >500 ms or a change from Screening (or from Baseline for *16159A-patients* and *16323A-patients*) in the QTcF interval >60 ms concurrently with a QTcF interval >470 ms
- the patient has a positive urine drug screen verified by repeated testing at the following site visit
- the patient fails to comply with study procedures
- the patient is <80% IMP compliant between two consecutive, scheduled visits
- the patient in the opinion of the investigator has significant risk of suicide or who answers "Yes" to suicidal ideation questions 4 or 5 or answers "Yes" to suicidal behaviour on the C-SSRS® at any time during the study

Patients who withdraw will not be replaced.

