12.4 Vital Signs and Weight

The PCS criteria used for vital signs and weight are the Lundbeck standard PCS criteria described in SOP_09978: *PV – PCS and standard reference values for laboratory investigations, vital signs and ECGs in clinical studies*, version 6, and are also included in [Table 2](#).

Descriptive statistics for the body measurements (weight, BMI, and waist circumference) in the Treatment Period, both absolute values and changes from baseline, will be presented by variable and week and the last assessment in the Treatment Period. The summaries for the absolute values will also include summaries for Baseline.

Descriptive statistics for the vital signs parameters, both absolute values and changes from baseline, will be presented by test and week and the last assessment in the Treatment Period. The summaries for the absolute values will also include summaries for baseline.

The number and percentage of patients with at least one PCS low value or PCS high value at any post-baseline assessment in the Treatment Period will be summarized by vital signs and body measurement parameter. All available assessments in the period will be included in the evaluation of PCS.

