S-LDL cholesterol, fasting	LDL	mmol/L		≥ 4.9
S-HDL cholesterol, non-fasting/unknown	HDL	mmol/L	≤ 0.8	
S-HDL cholesterol, fasting	HDL	mmol/L	≤ 0.9	
Cardiac/Skeletal/Muscle				
S-creatinine kinase (total)	CK	IU/L		≥ 400 (women) ≥ 750 (men)
S-creatinine kinase MB isoenzyme	CKMB	µg/L		≥ 8.5 or
	CKMBCK	%		≥ 3.5% of total CK
S-lactate dehydrogenase (total)	LDH	IU/L		≥ 750
S-troponin I	TROPONI	µg/L		≥ 1.5
S-troponin T	TROPONT	µg/L		≥ 0.4
Infection				
S-C-reactive protein	CRP	mg/L		≥ 25
S-globulin (total)	GLOBUL	g/L	≤ 15	≥ 55

Laboratory Test	CDISC Term	Unit	PCS Low	PCS High
Urine				
Urinary pH	PH		≤ 4	≥ 9

S=serum; B=whole blood; U=urine

Table 2 PCS Criteria for Vital Signs, Weight/BMI, and Waist Circumference

Variable	CDISC Term	Unit	PCS Low	PCS High
Waist circumference	WSTCIR	Cm	decrease ≥ 7%	increase ≥ 7%
Weight	WEIGHT	Kg	decrease ≥ 7%	increase ≥ 7%
Body Mass Index	BMI	kg/m ²	decrease ≥ 7%	increase ≥ 7%
Pulse rate, supine/sitting/unknown	PULSE	beats/min	< 50 and decrease ≥ 15	≥ 120 and increase ≥ 15
Diastolic blood pressure, supine/sitting/unknown	DIABP	mmHg	≤ 50 and decrease ≥ 15	≥ 105 and increase ≥ 15
Systolic blood pressure, supine/sitting/unknown	SYSBP	mmHg	≤ 90 and decrease ≥ 20	≥ 180 and increase ≥ 20
Orthostatic systolic blood pressure	OBP	mmHg	≤ -30	
Orthostatic pulse rate	OPR	beats/min		≥ 20
Temperature	TEMP	°C	decrease ≥ 2	≥ 38.3 and increase ≥ 2

Increase/decrease is relative to the baseline value.

Table 3 PCS Criteria for ECG Parameters

ECG Parameter	CDISC Term	Unit	PCS Low	PCS High
Absolute Time Interval				
PR interval	PRMEAN	Msec		≥ 260
QRS interval	QRS DUR	Msec		≥ 150
QT interval	QTMEAN	Msec		≥ 500
Derived Time Interval				
Heart rate	HRMEAN	beats/min	< 50 and decrease ≥ 15	≥ 120 and increase ≥ 15
QTcB interval	QTcB	Msec	< 300	> 500 or increase > 60
QTcF interval	QTcF	Msec	< 300	> 500 or increase > 60

Increase/decrease is relative to the baseline value.

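### The SAP's outlier counts start at a 30 mmHg orthostatic fall and at QTcF >500 ms or a rise >60 ms, leaving smaller excursions past the protocol's own entry limits without a row

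*SAP*

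**What the plan says.** **Orthostatic pressure.** Protocol 5.3 excludes all three entry groups on the same wording: "The patient has orthostatic hypotension (defined as a decrease in systolic blood pressure >20 mmHg between two measurements". Protocol 9.5.3 has pressure and pulse taken supine, sitting and standing. On the analysis side, SAP 12.4 states: "The PCS criteria used for vital signs and weight are the Lundbeck standard PCS criteria". Those limits are in Appendix III, Table 2. The row "Orthostatic systolic blood pressure" is low at −30 mmHg or below, and "Orthostatic pulse rate" is high at 20 beats/min or above. The absolute pressure limits apply to supine, sitting or unknown posture.

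**QTcF.** Table 3 flags values above 500 ms or an increase above 60 ms. The entry exclusion is "a QTcF interval >450 ms (for men) or >470 ms (for women". Protocol 5.4 withdraws a patient from treatment if "the patient has a QTcF interval >500 ms or a change from Screening" (Baseline for roll-over patients) exceeds 60 ms, the change counting only if QTcF is also above 470 ms.

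**What was already known.** Protocol 1.1.5.3 reports orthostatic hypotension as an adverse event in 19% of patients in the daily-dose cohorts of the multiple-ascending-dose study. It also reports a treatment- and dose-related QTcF trend, and then: "None of the patients in the study had any symptoms or QT cf values that met the potentially clinically significant (PCS) criterion". The criterion it gives is the one now in Table 3.

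**Status of the counts.** SAP 4.1 makes absolute values, changes and PCS values in vital signs and ECG primary endpoints. SAP 12.2 counts patients with at least one PCS value at any post-baseline assessment, excluding the safety follow-up visit.

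**The concern.** The primary objective is long-term safety, and orthostatic hypotension and QTcF are two cardiovascular signals the programme has already seen. For both, the categorical summary begins above the level the protocol treats as disqualifying at entry, and nothing is tabulated in between.

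PCS status also decides who enters the value listings and the listings of adverse events alongside values (SAP 12.2). A patient in the gap is missing from those as well, unless another limit is crossed.

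A second gap adds to this. No SAP section says whether the orthostatic difference is supine to standing or supine to sitting, or whether it is among the parameters given weekly descriptive statistics. SAP 4.1 and 12.4 do not name it. Even if it is included, weekly means do not show how many individuals had a marked fall.

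**Working it through.** The plan has no sample size, power or alpha figure on this point, so there is nothing to reproduce. The check compares the limits and then sizes the gap by illustration.

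**1. Orthostatic limits (whole mmHg).**
- Protocol entry definition: change < −20, so falls of 21 or more.
- SAP PCS: change ≤ −30, so falls of 30 or more.
- Meets the definition but not PCS: falls of 21 to 29. No other SAP table uses a 20 mmHg limit.

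**2. QTcF against the withdrawal rule.**
- Withdrawal: QTcF > 500, or (change > 60 and QTcF > 470).
- PCS: QTcF > 500, or change > 60.
- Each branch of the withdrawal rule implies PCS, so no patient can meet the rule without being counted. The reverse fails: 380 to 445 ms is a rise of 65, which is PCS but not a withdrawal case. The PCS limit is equal on the absolute value and wider on the change.

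**3. QTcF against the entry limits.**
- Men at 451–500 ms with a rise ≤ 60 ms, and women at 471–500 ms with a rise ≤ 60 ms, exceed the entry limit and are not PCS.
- Example: a man moving from 440 to 500 ms has a rise of exactly 60 and is not above 500, so no row counts him.

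**4. Size of the orthostatic gap per reading (assumed distributions).** With a single-visit change assumed normal, P(fall > 20) = Φ((−20 − mean)/SD) and P(fall ≥ 30) = Φ((−30 − mean)/SD).

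| Mean, SD (mmHg) | Fall > 20 | Fall ≥ 30 | Ratio | Share of >20 falls below 30 |
|---|---|---|---|---|
| −5, 10 | Φ(−1.5) = 6.7% | Φ(−2.5) = 0.6% | 11 | 91% |
| −3, 10 | Φ(−1.7) = 4.5% | Φ(−2.7) = 0.35% | 13 | 92% |
| −8, 12 | Φ(−1.0) = 15.9% | Φ(−1.83) = 3.3% | 5 | 79% |

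Over means 0, −5, −10 and SDs 8, 10, 12, 15, the last column runs from 64% (−10, 15) to 99% (0, 8).

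**5. Size per patient.** The SAP counts patients with any PCS value, and vital signs are scheduled at 15 post-baseline visits. If the 15 readings were independent (one extreme), P(any) = 1 − (1 − p)^15:
- −5, 10: 65% v 8.9%
- −3, 10: 50% v 5.1%
- −8, 12: 93% v 40%

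If a patient's readings were identical at every visit (the other extreme), the per-patient figures equal those in the table. The share of patients with a fall above 20 but none of 30 or more is the difference between the two columns. It is 56%, 45% and 53% under independence, and 6.1%, 4.1% and 12.5% under full dependence.

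**The case against.** The case against has real force.

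- **Entry limits are not outcome definitions.** The 20 mmHg and 450/470 ms limits are exclusion criteria, and no section makes them on-treatment endpoints. The PCS set is the sponsor's standard one and is looser than the entry limits elsewhere too: PR >250 v ≥260 ms, QRS >130 v ≥150 ms, ALT/AST >2 v ≥3 times the upper limit. This stands, and it is why the PCS rows should stay.
- **The signals have other routes.** The 19% is an adverse-event rate, and its like-for-like successor is planned in the adverse-event tables of SAP 12.1.6. Protocol 9.5.1 records events observed by the investigator or volunteered by the patient, so symptomatic cases do not depend on a measured value being judged significant. QTcF means and changes by week are in SAP 12.5, and a mean trend is better sought there than in an outlier count. This also stands. It leaves measured falls of 21–29 mmHg that produce no adverse event.
- **Any-visit counts can swell.** On the assumptions above, a >20 mmHg any-visit row could include half or more of patients, with no control arm to compare against. This is fair, and it argues for showing the count by visit as well.

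A reader might infer that the QTcF limit is laxer than the protocol's own on-treatment standard. Step 2 shows the opposite. A reader might also infer that patients with orthostatic hypotension go uncounted, or that the PCS table will be near zero. Falls of 30 mmHg or more are counted, adverse events are tabulated, and the patient-level figures run from 0.35% to 40% depending on assumptions. The documents support neither inference.

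The proposal is more than reviewer preference, because the SAP already reports below its PCS limits elsewhere. Section 12.3.2 tabulates ALT/AST above 2 times the upper limit, while PCS begins at 3 times.

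**Conclusion.** The point holds as a reporting gap, worth fixing but not an error in the PCS criteria. Falls of 21–29 mmHg meet the protocol's only definition of orthostatic hypotension and have no vital-sign outlier count of their own. These patients surface only through a recorded adverse event or another PCS limit, such as the orthostatic pulse row.

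For QTcF, the limit is consistent with the withdrawal rule. What is missing is a lower category, in a programme where this same criterion flagged nobody while a dose-related trend was present.

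The mismatch in limits follows from the documents alone. Its size does not: the 64%–99% share is per reading, and the patient-level gap of about 4% to 56% depends on the assumed means and SDs and on how strongly a patient's readings correlate.

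**What to change.** Keep every standard PCS row. Then:

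1. **SAP 12.4, derivation.** State how the orthostatic difference is calculated (supine to standing, and supine to sitting if used), and whether it receives weekly descriptive statistics.
2. **SAP 12.4, supplementary rows.** Give the number and percentage of patients with a systolic fall above 20 mmHg, by visit and at any post-baseline visit, among those without one at baseline.
3. **SAP 12.5, supplementary rows.** Give the number and percentage with post-baseline QTcF above 450 ms (men) or 470 ms (women), among those not above these limits at baseline.

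The cost is a few table rows from data already collected. The reported rates will look less favourable, and the any-visit counts will be inflated by repeated measurement with no control arm, so the text should say so. No clinical rule changes.

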Appendix IV

Study Flow Chart

Study Flow Chart

Study Procedures and Assessments

Visit	Screening ^a	Baseline ^b	Treatment Period														Primary Outcome or Withdrawal ^e	Safety Follow-Up ^d
			1	2	3	4	5	6	7	8	9	10	11	12	13	14		
Visit Number	1	2	3	4	5	6	7	8	9	10	11	12	13	14	15	16	17	18
End of Week	-	0	1	2	4	8	12	16	20	24	28	32	36	40	44	48	52	
Day	-14/-7	0	7	14	28	56	84	112	140	168	196	224	252	280	308	336	364	
Visit Window (days) ^f			±3	±3	±3	±6	±7	±7	±7	±7	±7	±7	±7	±7	±7	±7	±7	+3
Baseline Procedures and Assessments																		
Signed informed consent	√ ^a	√																
Diagnosis (DSM-5™)	√ ^a	√ ^f																
Demographics (age, sex, race)	√ ^a	√ ^f																
Relevant social, medical and psychiatric history	√ ^a	√ ^f																
Height	√ ^a	√ ^f																
Inclusion/exclusion criteria	√	√																
Effectiveness Assessments																		
PANSS	√	√ ^g	√	√	√	√	√	√	√	√	√	√	√	√	√	√	√	√
CGI-S	√	√ ^g	√	√	√	√	√	√	√	√	√	√	√	√	√	√	√	√
PSP	√	√ ^g			√					√								√
NSA-4		√ ^g			√					√								√
QLS		√ ^g			√					√								√
WoRQ		√ ^g			√					√								√
TooL		√ ^g			√					√								√
MSQ		√ ^g			√					√								√
HEA		√ ^h																√
Pharmacokinetic Assessments																		
Blood sampling for Lu AF35700 and metabolite assay		√ ^g			√					√								√
Translational Medicines Assessmentsⁱ																		
Blood sampling for gene expression profiling (RNA) ^j		√ ⁱ																√ ⁱ
Blood sampling for metabolomics/proteomics (plasma) ^j		√ ⁱ																√ ⁱ
Blood sampling for pharmacogenetics (optional) ^k		√ ⁱ																

Visit	Screening ^a	Baseline ^b	Treatment Period														Primary Outcome or Withdrawal ^c	Safety Follow-up ^d
			3	4	5	6	7	8	9	10	11	12	13	14	15	16		
Visit Number	1	2	3	4	5	6	7	8	9	10	11	12	13	14	15	16	17	18
End of Week	-	0	1	2	4	8	12	16	20	24	28	32	36	40	44	48	52	
Day	-14/-7	0	7	14	28	56	84	112	140	168	196	224	252	280	308	336	364	
Visit Window (days) ^e			±3	±3	±3	±6	±7	±7	±7	±7	±7	±7	±7	±7	±7	±7	±7	+3
Safety Assessments																		
Adverse events	√	√ ^l	√	√	√	√	√	√	√	√	√	√	√	√	√	√	√	√ ^m
Blood and urine sampling for clinical safety laboratory tests	√ ^a	√ ^g			√					√							√	√ ⁿ
Serum prolactin ^o	√ ^a	√ ^g			√					√							√	
HBA1c (fasting)	√ ^a	√ ^g			√					√							√	
Fasting blood glucose (P-glucose) and lipid profile (S-cholesterol, S-triglycerides, S-low density lipoprotein (LDL), S-high density lipoprotein (HDL))	√ ^a	√ ^g			√					√							√	
Vital signs	√	√ ^g	√	√	√	√	√	√	√	√	√	√	√	√	√	√	√	
ECGs ^p	√	√ ^g			√			√				√			√		√	
Body weight	√	√ ^g			√					√							√	
Waist circumference	√	√ ^g			√					√							√	
Physical Examination	√ ^a	√ ^g															√	
Abnormal movements rating scales (AIMS, BARS, mSAS)		√ ^g			√					√							√	
C-SSRS	√	√ ^g	√	√	√	√	√	√	√	√	√	√	√	√	√	√	√	
Other Study Procedures																		
IMP dispensed ^q		√	√	√	√	√	√	√	√	√	√	√	√	√	√	√		
Possible change in IMP dose ^q			√	√	√	√	√	√	√	√	√	√	√	√	√	√		
IMP returned and accountability			√	√	√	√	√	√	√	√	√	√	√	√	√	√	√	
Recent and concomitant medication	√	√ ^s	√	√	√	√	√	√	√	√	√	√	√	√	√	√	√	√
Urine drug screen	√ ^a	√ ^t															√	
Pregnancy test ^u	√ ^a	√ ^g			√					√							√	

- Screening Visit will be performed only for newly recruited patients and screening assessments marketed with an “a” will not be repeated at Baseline Visit. *16159A-patients* and *16323A-patients* will proceed from their lead-in study directly to the Baseline Visit. The ICF must be signed before any study related activities take place.
- For *16159A-patients*, the Baseline Visit will be performed the same day as the Primary Outcome Visit of study 16159A. For *16323A-patients*, the Baseline Visit will be performed the same day as the last day of the dosing period of study 16323A. The inclusion/exclusion criteria are confirmed based on the evaluation of the latest data available in the study 16323A or 16159A as applicable.
- This visit should take place as soon as possible after the patient withdraws from the study treatment.
- The Safety Follow-up Visit will be done 6 weeks (+3 days) after the last dose of IMP. This visit can be a telephone contact, unless an SAE has occurred since last visit or unless there was a clinically

significant abnormal safety laboratory test value at the last visit. In such cases, safety follow-up(s) must be scheduled to allow for a medical examination and/or blood sampling. Further Safety Follow-up Visits beyond 6 weeks may be needed as judged by the investigator (if further Safety Follow-up Visits are performed, these must be recorded in the patient's medical record, and not in the CRF).

- e. If the date of a patient visit does not conform to the study plan, subsequent visits should be planned to maintain the visit schedule relative to the Baseline Visit. The number of days between 2 visits should not exceed the number of days for which the patient has been dispensed IMP.
- f. For *16159A-patients* and *16323A-patients*, the data will be linked respectively from the Screening Visit in the study 16159A eCRF or from the Screening Visit in the study 16323A eCRF, when applicable.
- g. For *16159A-patients* and *16323A-patients*, results from effectiveness/safety assessments and blood/urine samples performed respectively at the Primary Outcome Visit (Visit 12) in study 16159A or at the last day of the dosing period (Day 42) in study 16323A (when available) will be linked to the Baseline Visit (Visit 1) in study 16159B, when applicable.
- h. For *16159A-patients*, HEA data will be linked from the Baseline A Visit in the study 16159A eCRF.
- i. To be performed only for newly recruited patients not previously participating in a study investigating Lu F35700.
- j. Exploratory gene expression profiling (RNA) and metabolomics/proteomics are covered by the main Patient Information Sheet.
- k. Sampling for pharmacogenetics is optional and a separate Patient Information Sheet covers this analysis. This sampling should preferably be at the Baseline Visit, but may be collected at any visit that includes a clinical safety laboratory sample.
- l. For *16159A-patients* and *16323A-patients*, on-going adverse events from study 16159A and 16323A, respectively, are to be transferred by the investigator to the eCRF, when applicable.
- m. Only for adverse events on-going at the Primary Outcome/Withdrawal Visit and new SAEs.
- n. Only to be taken if the laboratory test was clinically significantly abnormal at the Primary Outcome/Withdrawal Visit.
- o. Prolactin results will remain blinded throughout the study.
- p. For *16159A-patients*, additional ECGs will be done; 1 ECG recording before the daily dose is switched to weekly dosing (preferably on the day the decision of switching from daily to weekly dosing is taken) and 1 ECG recording the day after the first weekly dose is taken.
- q. The first dose of IMP should be taken after the Baseline Visit is completed. All treatment assignment and subsequent IMP assignment is done via the IVRS/IWRS. The IVRS/IWRS will be assessed at the unscheduled visit only if the dose adjustment requires dispensing of IMP.
- r. The dose of IMP can be increased for efficacy or decreased for tolerability at scheduled or unscheduled visits from Week 1 Visit.
- s. For *16159A-patients* and *16323A-patients*, on-going concomitant medication in study 16159A and 16323A, respectively, must be transferred by the investigators to the 16159B eCRF. All prescription, non-prescription medications, and herbal medications taken during study 16159B will be recorded as concomitant medications.
- t. Urine drug screen tests can be repeated any time during the study at the discretion of the investigator.
- u. S-βhCG pregnancy test should be performed at the Screening Visit (Only for *Other-patients*), Visit 5, Visit 10 and the Primary Outcome/Withdrawal Visit for women of childbearing potential. Urine pregnancy tests can be performed at any time during the study at the discretion of the investigator.
